10. A negative urine pregnancy and toxicology screen. Verbal affirmation will be obtained (i.e., “not pregnant” and “not currently using psychotropic drugs or during the past 3 months”) during the Screening Visit (Day 1). Urine screen will be obtained on Days 2 and 3. If subject reports that there is a “possibility that she is pregnant” on Day 1 (Screening Visit) a urine pregnancy screen will be performed on that day.
11. (Women): If stopped or started oral contraceptives recently, at least 60 days on/off oral contraceptives.

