Social Feedback Task: During the Social Feedback Task (presented on a personal computer) subjects are presented with their own picture along with a picture of a highly rated profile, along with feedback that they were liked (acceptance trial), not liked (rejection trial), or that others were undecided or had not yet rated them (neutral trial). Each run will consist of alternating condition blocks, with cross-hair fixation between blocks, similar to the fMRI study design from [name] previous projects. The total duration of the task is approximately 10 minutes. Questionnaires will be given before, during, and/or after the task to assess cognitive and emotional states. For questionnaires, answer choices may be presented on Likert scale (e.g., 5 discrete choices), or a visual analogue scale (e.g., a sliding scale), on paper or a computer. If time permits, subjects will perform an imagery training session (lasting about 2 minutes) in which they are asked to imagine that they are at their home computer. The purpose of this is provide a realistic scenario for them to imagine while they are performing the Social Feedback Task.

Balloon Analogue Risk Task: If time permits, subjects will also perform the Balloon Analogue Risk Task (BART). The BART is a computerized measure of risk taking behavior. Participants are presented with a cartoon balloon and offered the chance to earn points by pumping up the balloon by pressing a button. Each press causes the balloon to inflate and points to be added to a counter up until some threshold, at which point the balloon explodes and earnings are lost. Thus, the number of pumps is a measure of risk-taking.

Wheel of Fortune Task: If time permits, subjects will perform the Wheel of Fortune task (WoF). The WoF is a computerized measure of risk taking behavior. Participants are presented with a circle divided into two colors. The colors and sizes of the divisions represent different point values and probabilities. If the participant chooses correctly, they will win the points assigned to the chosen color. Otherwise, they don't get any points for the round. How frequently the participant chooses a low probability, high reward color is a measure of risk-taking.

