Stop Signal Task: If time permits, subjects will perform the Stop Signal Task (SST). The SST is a computerized measure of response inhibition and attention. During the task, participants are instructed to quickly identify and respond to stimuli presented (e.g., the direction of an arrow). Occasionally, participants will receive a cue indicating that they are to withhold their response. Response times and correct/incorrect responses are collected.

Emotion Face Recognition Task: If time permits, subjects will perform a task requiring them to identify the emotion type or intensity depicted on pictures of faces. This task will allow the measurement of emotion recognition bias.

tDCS: The intervention, tDCS, is commercially available and consists of a small battery-driven device connected to electrodes. The scalp is inspected for any pre-existing irritation, cuts, or lesions to avoid stimulating over damaged skin. Subjects are seated comfortably (or lying in the scanner), and the locations of electrode placements are identified using landmarks on the head (e.g., using the EEG 10-20 system). Stimulation begins with a brief “ramping up” period (potentially resulting in a tingling sensation on the scalp) when the stimulation is gradually increased to the desired current (up to 2 mA), and “ramp down” period. By way of comparison, small hearing aids run on approximately 2.4 millamps. The sham condition may consist of stimulation through a different electrode placement (up to 30 minutes; up to 2 mA) or with a shorter duration (up to 2 minutes) than the active condition. This sham procedure has been shown to be indiscernible from active tDCS. In the active condition, the current will be maintained for the duration of the block (up to 30 minutes).

tDCS-only study: Testing will occur over two sessions (sham or active, counter-balanced order between subjects). The two sessions will be separated by at least 5 days in order to minimize potential carry-over effects. In each session, tDCS (or sham) will begin prior to the Social Feedback Task, and may be maintained for the duration of the task or cease before the Social Feedback Task begins.

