tDCS+fMRI study: Testing will occur over two sessions (sham or active, counter-balanced order between subjects). The two sessions will be separated by at least 5 days in order to minimize potential carry-over effects. In each session, tDCS (or sham) will occur prior to or concurrent with fMRI scanning and the Social Feedback Task. Structural and resting state fMRI will also be acquired during this session.

Questionnaires (administered in person or over internet): Adult Rejection Sensitivity Questionnaire, Brief Fear of Negative Evaluation Scale, Brief Resilience Scale, Difficulties in Emotion Regulation Scale, Ego Resilience Scale, Emotion measures following social feedback, Emotion Regulation Questionnaire, Hurt Feelings, Interpersonal Sensitivity Measure, Mini Mental State Exam, Multidimensional Scale of Perceived Social Support, PANAS-X, Rosenberg Self-Esteem Scale, Ruminative Responses Scale, Sensitivity to Rejection Scale, Social Feedback/tDCS Follow-up, Social Resilience Scale, Sociability Survey, State Self-Esteem, Structured Clinical Interview or MINI International Neuropsychiatric Interview, tDCS Sensation Questionnaire, Teasing Questionnaire-Revised, Visual Analogue Scale, State Rumination Measure. For questionnaires, answer choices may be presented on Likert scale (e.g., 5 discrete choices), or a visual analogue scale (e.g., a sliding scale), on paper or a computer.

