## **E. Data Analysis**

tDCS-only: Measures of cognitive and emotional states will be compared within subjects for sham vs. active tDCS. These changes may also be correlated with trait measures.

**tDCS+fMRI:** Our fMRI data will be analyzed with Statistical Parametric Mapping v.8 (SPM8). We will first conduct a hypothesis-driven region of interest (ROI) analysis (Bonferroni-corrected alphas for multiple VOIs) to examine brain areas previously shown to be activated during rejection including the rVLPFC, anterior insula, and dorsal anterior cingulate. We will compare rejection-neutral contrasts between runs and sessions, in a within-subjects analysis. We will also conduct a whole-brain analysis in a voxel-by-voxel brain-wide search. Statistical parametric maps are obtained using whole-brain image subtraction routines with the images warped to MNI standardized space. Differences between tDCS and sham are then mapped into stereotactic space using t-maps of statistical significance using a general linear model. RS as a covariate will also be tested in both the VOI and whole-brain analyses.

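### Session order is counter-balanced in both aims, but Section E puts no session or order term in the sham versus active comparison, which costs power if responses shift between sessions

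*Combined protocol and SAP*

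**What the plan says.** Section D.5 (Procedures) gives the tDCS-only study two sessions per subject, one sham and one active, with order counter-balanced: "Testing will occur over two sessions (sham or active, counter-balanced order between subjects". The imaging study has the same design: "tDCS+fMRI study: Testing will occur over two sessions (sham or active, counter-balanced order between subjects". The gap between sessions is justified on one ground only: "The two sessions will be separated by at least 5 days in order to minimize potential carry-over effects". Section D.1 allows up to 30 subjects per aim, in separate groups.

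The analysis is in Section E. For Aim 1: "Measures of cognitive and emotional states will be compared within subjects for sham vs. active tDCS", with optional correlations against trait measures. For Aim 2: "We will compare rejection-neutral contrasts between runs and sessions, in a within-subjects analysis". The only covariate named is RS: "RS as a covariate will also be tested in both the VOI and whole-brain analyses". No session, period, order or sequence term appears in Section E or anywhere else in the document. The Aim 2 reference to sessions does not supply one. Each subject's two sessions are the sham and the active session, so comparing sessions is the treatment contrast itself, not an adjustment for first versus second visit.

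**The concern.** Subjects do the Social Feedback Task in both sessions. Previous tDCS experience is an exclusion (Section D.4), so the first session is their first full stimulation, and by the second session they have already met the task and its feedback. A general change in response from the first session to the second is plausible. A gap chosen to limit carry-over of stimulation does not remove it.

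Counter-balancing makes such a change cancel in the mean when the two orders are equal in size. It does not take the change out of the variance of the paired differences unless the analysis uses the order. A design that balances a factor and an analysis that ignores it give away precision, and with at most 30 subjects per aim there is little to spare. If subjects are lost unevenly between orders, the cancellation is also incomplete. Loss between sessions is possible because eligibility is checked again at each one: "Urine screen will be obtained on Days 2 and 3".

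For Aim 2 only a shift in the rejection-minus-neutral contrast matters, because a shift common to both conditions cancels. The same would hold for Aim 1 if mood were scored as that difference. Section E names no contrast for Aim 1, and the timing of the mood measures is open: "Questionnaires will be given before, during, and/or after the task to assess cognitive and emotional states".

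**Working it through.** The documents contain no power calculation, effect size or SD, so there is no planned figure to reproduce.

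**Inputs from the documents:** two sessions per subject, counter-balanced order (D.5); up to 30 subjects per aim (D.1).

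**Assumptions, none in the documents:** two-sided 0.05; 15 subjects per order; normal paired differences; no carry-over; true effect τ = 0.529 SD of the paired difference, which gives a paired t-test on 30 subjects 80% power when there is no shift; session shift π from 0 to 1.0, in the same SD units.

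**Model.** Let π be the second-session minus first-session shift. The active-minus-sham difference has mean τ + π for subjects who have sham first and τ − π for those who have active first, with SD 1 within each order.

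- *Unadjusted:* paired t-test on all n differences, n − 1 df.
- *Adjusted:* unweighted mean of the two order-specific mean differences, with pooled within-order SD and n − 2 df. For complete pairs this equals a model with treatment, session and subject.

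**Equal orders.** The unadjusted mean is unbiased, but its estimated SE is inflated by √(1 + π²·n/(n − 1)). At π = 0.5 and n = 30 this is √(1 + 0.25 × 30/29) = 1.122, equivalent to 30/1.122² = 23.8 subjects. Results of simulation with 100,000 or more trials per cell:

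| Shift π (SD) | Power, unadjusted | Power, adjusted | Type I error, unadjusted |
|---|---|---|---|
| 0.1 | 80% | 80% | 4.8% |
| 0.25 | 78% | 80% | 4.3% |
| 0.5 | 72–73% | 80% | 2.9% |
| 0.75 | 63% | 80% | 1.5% |
| 1.0 | 50% | 80% | 0.6% |

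The adjusted type I error is 5% throughout. The pattern holds for other effects: at π = 0.5, power is 47% versus 56% for τ = 0.4 and 84% versus 89% for τ = 0.6.

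**Unequal completers.** The unadjusted bias is π(n₁ − n₂)/n.

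- 15/13: 2/28 = 0.071π, or 0.04 SD at π = 0.5.
- 15/11: 4/26 = 0.154π, or 0.08 SD at π = 0.5.

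The adjusted estimate has no bias in either case.

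**Coding of order in Aim 2.** With order coded +1/−1 and left uncentred, the intercept of the second-level model is the unweighted mean of the two order-specific differences. If order is mean-centred, the intercept is the raw mean difference, so the bias stays while the residual SD shrinks. At 15/11 under the null, type I error is:

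| Shift π (SD) | No order term | Uncentred order | Mean-centred order |
|---|---|---|---|
| 0.5 | 4.1% | 5% | 6.6% |
| 1.0 | about 2.4% | 5% | about 12% |

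**Cost when there is no shift** (noncentral t, unadjusted versus adjusted power): 80.0% versus 79.9% at 15/15; 77.0% versus 76.7% at 15/13; 73.7% versus 72.5% at 15/11.

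**The case against.** The case for leaving the plan alone has several parts.

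- Section E is brief and names no test for Aim 1. It is silent on session rather than committed to an unadjusted analysis. This is true, but silence leaves the choice to be made after the data are seen.
- The loss depends on a shift the documents do not quantify, and for Aim 2 it must be a shift in the rejection-minus-neutral contrast. An optional example stimulation on Day 1, optional imagery training and subjects' knowledge that the ratings are not real could all limit first-session novelty. None of these shows the shift to be small, but the dependence stands.
- At near-balanced orders the unadjusted test errs on the safe side. Even at 15/11 its false-positive rate stays below 5%. It takes a split such as 20/10 with a 0.5 SD shift to raise it to about 10%, and no dropout rate is given. This stands: the main stake is power, with modest bias second.
- Aims 1 and 2 allow other regions, in either hemisphere, to be stimulated in separate subjects, so the 30 may be divided. In very small cells the lost degree of freedom matters. With effects set for 80% unadjusted power and no shift, adjusted power is 78.7% at n = 10 and 74.8% at n = 6. At n = 6 with a 0.25 SD shift, adjusting costs about 3 points. This stands, but such cells are hypothetical.
- The figures use 0.05, whereas the Aim 2 ROI tests are Bonferroni-corrected. At 0.05/3 the gap at a 0.5 SD shift is wider: 53% versus 64%.
- Section F describes a pilot intended to produce preliminary data. That lowers the priority but does not make the unadjusted analysis the better one.

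**Conclusion.** The point holds. Both aims counter-balance session order, and nothing in the document puts session or order into the sham versus active analysis. The consequence is conditional. At a shift of 0.25 SD of the paired difference or less, the loss is about 2 points of power and matters little. At 0.5 SD it is about 7 points, and at 1.0 SD about 30, under the assumed effect of 0.53 SD, 15 subjects per order and two-sided 0.05. With equal orders the danger is a missed effect, not a false positive. With unequal completers a small part of the shift also remains in the estimate. This does not make the study invalid. It is an inexpensive improvement that should be made before analysis.

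**What to change.** Add to Section E:

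- **Aim 1:** analyse sham versus active with treatment and session (first or second) as fixed effects and subject as a random effect. Subjects with only one session can contribute to this model. State which mood score is analysed, so that it is clear whether a shift common to both task conditions cancels.
- **Aim 2:** in the second-level model of the active-minus-sham difference in the rejection-minus-neutral contrast, which needs both sessions, enter order coded +1/−1 without mean-centring and test the intercept. RS may be mean-centred in the same model; order must not be.
- **Both aims:** report the number of completers in each order.

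The cost is a few lines of text and one degree of freedom. If the 30 subjects are split into very small groups by stimulation region, the degree of freedom costs more, and the plan should say in advance how those groups are analysed.

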### A. Specific Aims

Aim 1: *To test the behavioral effects of tDCS during social rejection.* The first step will be to obtain behavioral effects of transcranial direct current stimulation (tDCS) during social rejection without functional magnetic resonance imaging (fMRI). Whereas previous studies used Cyberball (a computerized ball-tossing game that simulates social exclusion), we will use the Social Feedback Task. This task was created by [name] to be more ethologically-relevant, has been shown to sustain negative moods during rejection, and activates the right ventral lateral prefrontal cortex (rVLPFC) (preliminary fMRI data from 50 healthy controls in [name] previous study). Anodal tDCS will be applied over the right or left VLPFC to measure changes in mood during rejection and neutral conditions. Depending on results, alternate regions in separate subjects may also be stimulated: dorsolateral prefrontal cortex, insula, anterior cingulate cortex, pre-supplementary, and supplementary motor area [all regions may be right or left hemisphere]. All of these regions have been shown to be involved in emotion regulation. Questionnaires will be given before, during, and after the task to assess cognitive and emotional states.

Aim 2: *To identify neural pathways regulating negative moods during social rejection, using tDCS for activation and fMRI for assessment.* Using a cross-over, sham-controlled design similar to previous tDCS+fMRI studies, we will measure the effects of anodal tDCS over the right or left VLPFC on neural activity and negative mood during rejection and neutral conditions. Alternate regions in separate subjects may also be stimulated including the dorsolateral prefrontal cortex, insula, anterior cingulate cortex, pre-supplementary, and supplementary motor area [all regions may be right or left hemisphere]. All of these regions have been shown to be involved in emotion regulation.

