## **G. Human Subjects Research Protection from Risk**

**tDCS risks and minimization of risk:** tDCS is performed by placing electrodes upon the scalp and applying a small electrical current in order to affect brain function. The maximum amount of current that subjects would receive in our study is 2 milliamps, and each tDCS session can last up to about 30 minutes. As a point of reference, small hearing aids run on approximately 2.4 milliamps. At this level of current and duration of tDCS stimulation, possible side effects are expected to be mild, benign, and short-lived. In a review of 74 studies reporting adverse effects of tDCS, the most common side effects were itching (39%), tingling (22%), headache (15%), burning sensation (9%), and discomfort (10%).

Other studies have shown that tDCS does not elevate serum levels of molecular markers of neuronal injury such as neuron-specific enolase or N-acetyl-aspartate. Both contrast-enhanced MRI and EEG studies have found no pathological changes associated with application of tDCS. In contrast to other forms of transcranial electrical stimulation such as transcranial magnetic stimulation (TMS), tDCS has never been shown to cause epileptic seizures, even in patients with refractory epilepsy. Finally, certain electrode positions, specifically those close to the mastoid process (the raised part of the skull behind the ear), can sometimes influence the vestibular system and cause nausea and/or vertigo. Our staff is well trained in proper administration of tDCS, and the electrode positions to be used in this study will not be near the mastoid process.

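### For both aims the plan fixes only a counter-balanced session order; random sequence generation, concealment and masking of staff are not specified

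*Combined protocol and SAP*

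**What the plan says.** All references are to the combined protocol and SAP.

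- **Design and order.** Section A (Specific Aims) describes Aim 2 as follows: "Using a cross-over, sham-controlled design similar to previous tDCS+fMRI studies". Section D.5 gives the order rule for Aim 1, "Testing will occur over two sessions (sham or active, counter-balanced order between subjects", and repeats it for Aim 2: "tDCS+fMRI study: Testing will occur over two sessions (sham or active, counter-balanced order between subjects". No method of assigning the order is given, and no one is named as holding a list.
- **Sham.** Section D.5 allows two kinds: "The sham condition may consist of stimulation through a different electrode placement (up to 30 minutes; up to 2 mA"), or a shorter stimulation of up to 2 minutes, against up to 30 minutes in the active condition. It then states: "This sham procedure has been shown to be indiscernible from active tDCS".
- **Staff.** Section G says "Our staff is well trained in proper administration of tDCS". No section says that the operator, the person running the task, the person giving the questionnaires or the image analyst is masked.
- **Outcome.** Section D.5 says "Questionnaires will be given before, during, and/or after the task to assess cognitive and emotional states". Answers may be on a Likert scale "or a visual analogue scale (e.g., a sliding scale), on paper or a computer".
- **Scheduling.** Section D.5 notes that hormone changes over the menstrual cycle may affect mood, and allows session dates to be set with cycle phase in mind.
- **Analysis.** Section E compares states within subjects, sham against active, and states no period or sequence term.

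**The concern.** Counter-balancing fixes how many subjects receive each order. It does not say how the next subject's order is chosen. Strict alternation satisfies it, and so does a coordinator picking the order that keeps the totals level. This leaves two risks, which should be kept apart.

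1. **Predictable order.** If the order is known or guessable when dates are booked, the choice of dates can become tied to condition. The protocol itself treats menstrual phase as relevant to mood and allows scheduling to depend on it, so this is a concrete route by which phase and condition could be confounded.
2. **Staff knowledge of condition.** Whoever places the electrodes or sets the device would know which session is active unless a masking step is added. Subjects are asked to imagine that ratings they know to be invented are real, so their engagement may respond to how staff instruct them. A cue that differs between active and sham sessions goes straight into the within-subject contrast. Neither the use of each subject as their own control nor an even split of orders removes it.

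At stake is whether an active-sham difference in mood can be attributed to the stimulation.

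**Working it through.** **Plan's own figure.** There is none to reproduce: no effect size, SD, power or alpha is stated for the active-sham comparison in mood.

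**Step 1: what the text covers.** The sham sentence concerns how the stimulation is perceived and describes no staff procedure. It stands beside two physically different shams. A different electrode placement is visible to anyone present who knows the intended site. A shorter duration is known to whoever sets the device.

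**Step 2: illustration of the effect of a cue.** Inputs: n = 30 (section D.1 gives up to 30 per aim, so this is a ceiling); two-sided alpha 0.05 (assumed); true effect zero; bias b of 0.1, 0.2 or 0.3 SD of the within-subject difference (assumed).

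The standard error of the mean difference is 1/√30 = 0.183 SD. The paired t statistic then follows a noncentral t distribution with n − 1 = 29 degrees of freedom and noncentrality b√n, which is 0.1 × 5.477 = 0.548, 0.2 × 5.477 = 1.095 and 0.3 × 5.477 = 1.643. The false-positive rate is the probability that |t| exceeds the two-sided 5% critical value:

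| n | b = 0 | b = 0.1 | b = 0.2 | b = 0.3 |
|---|---|---|---|---|
| 30 | 0.050 | 0.083 | 0.185 | 0.355 |
| 20 | 0.050 | 0.071 | 0.136 | 0.247 |
| 15 | 0.050 | 0.065 | 0.112 | 0.192 |

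For scale, the smallest true effect detectable with 80% power at n = 30 is about 0.53 SD, so a bias of 0.2 to 0.3 SD would be roughly 0.2/0.53 = 38% to 0.3/0.53 = 57% of it.

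**Step 3: order imbalance.** Suppose k of n subjects have active first, and the second session differs from the first by an additive amount P. Active-first subjects carry −P in their active-sham difference and the others carry +P. The unadjusted mean is therefore shifted by P(n − 2k)/n, of size |2k − n|/n times P:

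- 15:15 gives 0/30 = 0
- 18:12 gives 6/30 = 20% of P
- 20:10 gives 10/30 = 33% of P

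An exact split thus cancels an average session effect. Balance over a whole aim does not ensure balance within a stimulation site, and section A allows alternate sites in separate subjects. Unrestricted randomization would not be a good substitute: with 30 subjects, a split of 20:10 or worse occurs with probability 0.099. This is the reason to use blocks.

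**The case against.** The strongest reply is that the documents are silent, not adverse. A reader might infer that allocation is not random and that staff are unmasked. The text does not say so: a counter-balanced order is compatible with a random balanced list, and a design label on the title pages, which were not available here, could say more. This stands, and the point is worded as not specified.

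A reader might also picture one person who sets the current, coaches the subject and takes mood ratings face to face. The documents do not support this either. Roles are not assigned, and state ratings may be completed on paper or computer. Self-completion limits direct influence at the moment of rating; it does not limit cues given earlier, during set-up and instruction.

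Nor does a non-random order itself create expectation bias. That comes from knowledge of the condition, and a random list with an unmasked operator would leave it unchanged. Every subject receives both conditions, so a predictable order has less scope for selection bias than in a parallel-group trial. Scheduling by cycle phase could equally serve to hold phase constant across the two sessions. The link to condition is therefore a possibility that the plan leaves open and does not show to have happened.

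Finally, section D.5 lists a tDCS Sensation Questionnaire, which could help to show whether the sessions felt different. Section E plans no analysis of it, so it does not close the gap.

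**Conclusion.** The concern holds as a gap in the design as written. For both aims, following the plan to the letter permits a predictable order and handling of self-rated mood by staff who know the condition. It should be corrected, although it does not show that the comparison is biased.

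The size is illustrative. The range of about 8% to 36% rests on an assumed bias of 0.1 to 0.3 SD, an assumed two-sided alpha of 0.05 and the full 30 subjects; a reader should not take 36% as the trial's error rate. With 15 subjects the same bias gives about 6.5% to 19%. The 20% and 33% leaks of a session effect arise only if the split drifts to 18:12 or 20:10. At 15:15 the leak is zero, and balance is the one feature that the plan does promise.

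**What to change.** - Replace the counter-balancing rule with a computer-generated, permuted-block random order for each aim, and within stimulation site if more than one is used. Prepare the list before the first subject, and release each subject's order only after both session dates are fixed.
- Have an existing team member who neither runs the task nor collects ratings set the condition.
- Mask the staff who run the task and collect ratings wherever the sham allows it. If the sham uses a different electrode placement, either hide the placement from them or state that those sessions are unmasked for staff; dividing the tasks is not enough by itself.
- Process the images under coded session labels.
- Add a period term to the active-sham comparison in section E.

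This needs a short amendment and no additional subjects. The cost is slightly less freedom in scheduling and a division of tasks among existing staff, which a study on a pilot grant will need to confirm it can manage.

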### B. Background and Significance

Social acceptance into groups and intimate relationships are necessary for survival and emotional well-being. Actual or perceived threats to this need can produce strong negative moods and social withdrawal.

Neuroimaging studies by [name] and several others have identified brain regions activated during social rejection (i.e., when one is not wanted or liked). However the cause-and-effect of these activations is unclear: are they activated to enhance negative affect, or do they activate in order to decrease negative affect?

Recent studies have attempted to answer this by using tDCS, a safe and non-invasive form of neurostimulation that affects neuronal excitability. These studies provided tDCS over the rVLPFC, a region previously shown to be associated with *diminished* distress during rejection, and found that anodal tDCS reduced hurt feelings and aggression, whereas cathodal tDCS (producing the opposite current) increased hurt feelings during rejection. Importantly however, these studies did not examine the neural mechanisms associated with these changes. The **goal** of the present study is to activate and identify neural pathways regulating negative moods during rejection by combining tDCS and fMRI in a sample of healthy volunteers.

Whereas tDCS affects neuronal excitability, tDCS combined with fMRI has the potential to allow for causal inferences about neural activity and behavior. At the end of this project, we will have identified neural pathways regulating mood during social rejection. This will provide preliminary data for future projects that will combine tDCS and fMRI for investigating dysregulated responses to rejection in psychiatric populations such those with major depressive, social anxiety, and borderline personality disorders. Data from this study may also provide a rationale for testing tDCS as a safe, novel, inexpensive, non-pharmacological, and non-invasive treatment for these disorders.

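### Aim 2 promises neural pathways that regulate mood, but the planned imaging analyses test only activation differences: none tests coupling between regions, links imaging to mood, or uses the resting-state data

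*Combined protocol and SAP*

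**What the plan says.** **The promise.** Section A states Aim 2 as: "To identify neural pathways regulating negative moods during social rejection, using tDCS for activation and fMRI for assessment". Section B gives the expected result without qualification: "At the end of this project, we will have identified neural pathways regulating mood during social rejection". Section A also names two kinds of outcome for Aim 2: "we will measure the effects of anodal tDCS over the right or left VLPFC on neural activity and negative mood during rejection and neutral conditions".

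**The data.** Section D.5, under the tDCS+fMRI study, describes two sessions per subject, one active and one sham, and adds: "Structural and resting state fMRI will also be acquired during this session". Resting-state imaging is mentioned nowhere else in the documents.

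**The analysis.** The tDCS+fMRI paragraph of section E plans:
- a region-of-interest analysis with Bonferroni correction, naming the rVLPFC, the anterior insula and the dorsal anterior cingulate;
- within-subject comparison of rejection-minus-neutral contrasts across runs and sessions;
- a whole-brain voxelwise search: "Statistical parametric maps are obtained using whole-brain image subtraction routines with the images warped to MNI standardized space";
- t-maps of tDCS against sham from a general linear model;
- RS as a covariate in both the regional and the whole-brain analyses.

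The only comparison of emotional measures between active and sham is in the tDCS-only paragraph, which serves Aim 1.

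**The concern.** A contrast at a region or voxel shows where mean signal differs between conditions. It does not show whether stimulating one region alters its coupling with another, and it does not show that a neural change goes with a change in mood. The stated conclusion needs at least the second of these. It also needs the first if a pathway means a connection between regions.

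If the plan is followed exactly, either the Aim 2 conclusion is reported without an analysis behind it, or a connectivity or brain-mood analysis is chosen after the data are seen. Seed, targets, mood measure and scan could then all be picked with the results in view. Section F says the pilot is to supply preliminary data for external funding, and section B says it may provide a rationale for testing tDCS as a treatment. An unsupported pathway claim would carry into both.

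**Working it through.** **Step 1: set the claim against each planned analysis.**

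| Planned imaging analysis (section E) | Tests coupling? | Relates imaging to mood? | Uses resting-state data? |
|---|---|---|---|
| Region-of-interest contrast | No | No | No |
| Rejection-minus-neutral across runs and sessions | No | No | No |
| Whole-brain voxelwise subtraction | No | No | No |
| tDCS-versus-sham t-maps | No | No | No |
| RS as covariate | No | No | No |

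The covariate analysis is a regression on the activation contrasts. Its predictor is RS, not the active-minus-sham change in mood. Section E does name the software for the fMRI data in general terms, but gives no model, measure or contrast for resting state. The structural images may serve spatial normalisation, so the unused data are the resting-state scans: 30 subjects × 2 sessions = 60 at most, if they are acquired at both sessions.

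**Step 2: what could the missing analyses detect?** The documents give no power, effect size or numeric alpha, and no derivation of the sample size, so there is no figure to reproduce. I assume two-sided tests and 80% power. Section D.1 gives up to 30 subjects for Aim 2.

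*Active versus sham, paired t-test.* With dz = mean difference / SD of differences, power = P(T′ > t(1−α/2, n−1)), where T′ is noncentral t with n−1 degrees of freedom and noncentrality dz√n. Solving for 80%:

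| n | alpha | critical t | dz |
|---|---|---|---|
| 30 | 0.05 (one uncorrected test) | 2.045 | 0.53 |
| 30 | 0.05/2 = 0.025 (two targets) | 2.364 | 0.59 |
| 30 | 0.05/3 = 0.0167 (three named regions) | 2.541 | 0.62 |
| 15 (assumed to share a site) | 0.025 | 2.510 | 0.88 |

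At dz = 0.53 and n = 30, power is 0.80 uncorrected, 0.70 at alpha 0.025 and 0.64 at alpha 0.0167.

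*Imaging change against mood change, correlation.* Minimum |r| = tanh[(z(1−α/2) + z(0.80)) / √(n−3)].
- n = 30, alpha 0.05: (1.960 + 0.842)/√27 = 0.539, so |r| = 0.49.
- n = 30, alpha 0.0167: (2.394 + 0.842)/√27 = 0.623, so |r| = 0.55.
- With an assumed 27 or 24 completers, |r| rises to 0.52 or 0.55 at alpha 0.05, and to 0.58 or 0.61 at alpha 0.0167.

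**Step 3: is a connectivity analysis well defined as things stand?** Two items must be settled. Section A allows the right or left VLPFC and several alternate regions in different subjects, so a seed at the stimulated site may not be common to all 30. Section D.5 lets stimulation precede or overlap scanning and does not place the resting-state scan relative to it, so an active-versus-sham resting comparison could mix timing with treatment.

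**The case against.** The best defence is that the protocol never defines a pathway. Section B rests its inference on perturbation: stimulate, then image, with sham as control. On that reading, a change in the anterior insula or dorsal anterior cingulate under VLPFC stimulation is evidence of a downstream effect, and section E supplies the matching contrasts. This stands in part. A reader might infer that the planned analyses can say nothing beyond the stimulated site, or that no version of the Aim 2 conclusion could follow. The documents do not support that, because the sham-controlled crossover can show activation changes in distant regions. But even if a pathway is only a set of regions, the claim that it regulates mood remains untested.

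A second defence is that this is a departmental pilot, in which collecting scans without a confirmatory plan is not itself an error. That is fair. The fault lies in the unqualified conclusion in section B, and a pilot can narrow its claim.

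Third, adding connectivity alone would not close the gap, since coupling by itself says nothing about mood. That is right, so the remedy needs a brain-mood analysis as well.

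Finally, a reader might infer that a connectivity test would have the same sensitivity as the planned activation test. That holds only if neither is corrected. Section E corrects the regional tests, and with correction the detectable dz is 0.62 for three regions against 0.59 for two connectivity targets, provided all 30 subjects share a seed.

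**Conclusion.** The point holds as a mismatch between claim and analysis. None of the five planned imaging analyses tests coupling, none relates imaging change to mood change, and the resting-state scans have no stated use. The plan can support the statement that tDCS changed rejection-related activation in certain regions, near or far. It cannot support the statement that pathways regulating mood were identified.

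The activation contrasts are not put in question by this point, so it should be corrected but does not undermine the trial. The comparison of claim and plan rests on the text alone. The sensitivity figures rest on my assumed power, alphas and numbers per site, and show only that any added tests would detect moderate to large effects.

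**What to change.** In section E, pre-specify:

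1. **Coupling.** A psychophysiological interaction (rejection versus neutral) seeded at the stimulated site, compared active versus sham within subject among subjects who share that site. Use the anterior insula and dorsal anterior cingulate as targets, each at alpha 0.05/2.
2. **Link to mood.** An analysis relating each subject's active-minus-sham change in the regional or connectivity measure to the same subject's active-minus-sham change in negative mood, with both measures named in advance.
3. **Resting state.** Label seed connectivity exploratory, and compare active with sham only if the scan's timing relative to stimulation is the same in both sessions.

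If the sponsor does not want these, reword Aim 2 in section A and the matching sentences in section B so that the study identifies regional activation changes under tDCS versus sham.

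No new scans, visits or subjects are needed. The cost is a little more analysis time, a record of stimulation site and scan order, and a small added test family with limited sensitivity. Item 2 would support a link between neural and mood change but would not by itself establish mediation. Rewording costs nothing.
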